9.0 Efficacy Analyses

9.1 General Considerations

All efficacy analyses will be conducted in ITT Population in each period. All tests will be 1-sided at an alpha level of 0.05.

The Primary Analysis will be conducted after all ongoing subjects have completed Week 12, data pertaining to Period 1 has been cleaned, and a database lock has occurred for the purpose of efficacy and safety analysis in Period 1. This is the only and final efficacy analysis for Period 1.

In Period 1, all categorical variables at Week 12 and experience of flare in Period 1 will be analyzed using one sample Chi-square test comparing with historical placebo rate. Supplemental analyses will be conducted to compare in-trial data in upadacitinib group vs in-trial placebo data combined with historical placebo data for primary and secondary endpoints, and compare in-trial data in upadacitinib group vs in-trial placebo data for all categorical endpoints.

Continuous variables will be analyzed using Mixed-Effect Model Repeat Measurement (MMRM) (for endpoints other than DLQI) and Analysis of Covariance (ANCOVA) (for

DLQI) comparing with historical placebo mean change from Baseline at Week 12. Supplemental analyses will be conducted to compare in-trial data in upadacitinib group vs in-trial placebo data.

Long-term efficacy in the Period 2 will be summarized using the observed case approach.

Any subject who is randomized based on a wrong stratum will be analyzed according to the actual stratum the subject belongs to.

For variables other than PGA Skin Pain NRS, "Baseline" refers to the last non-missing observation on or before the date of the first administration of study drug or the date of randomization if no study drug is given. The "Baseline" of PGA Skin Pain NRS is defined as the last non-missing weekly average score, calculated based on the daily scores from the past 7 days (with non-missing values in 4 or more days of the 7 day period), before the date of the first administration of study drug or on or before the date of randomization if no study drug is given.

9.2 Handling of Missing Data

Missing data could occur due to various reasons, including missing visits/assessments, early withdrawal from the study, or missing due to COVID-19 infection or logistic restriction.

The COVID-19 pandemic is interfering with the conduct of many ongoing trials, with potential impacts on treatment duration and the collection, analysis and the interpretation of clinical trial data. Some protocol-specified visits in the clinical trials may be impacted due to COVID-19 infection or logistical restrictions during the pandemic. For example, some scheduled visits may be missed due to self-quarantine or local government restrictions on travel; some visits may also be delayed or canceled due to healthcare resource constraints during the pandemic. Impacted visits due to COVID-19 will be recorded in the database. The probability of having missed visits and missing data due to COVID-19 infection or logistical restrictions related to the COVID-19 pandemic can be reasonably assumed to be unrelated to the unobserved values. Therefore, for the purpose

of statistical analysis, it is reasonable to assume that these missing data are missing at random (MAR) and the statistical models that require MAR assumption are appropriate. Sensitivity analyses will be performed to assess the impact of missing data and the robustness of the conclusion.

Handling of intercurrent events and missing data for the efficacy analyses is described below.

9.2.1 Categorical Endpoints in Period 1

- The primary approach for handling missing data in the analysis of categorical endpoints (including the primary endpoint) will use **Non-Responder Imputation** while incorporating Multiple Imputation (MI) to handle missing data due to **COVID-19 (NRI-C)**.

The NRI-C will categorize any subject who does not have an evaluation during a pre-specified visit window (either due to missing assessment or due to early withdrawal from the study) as a non-responder for the visit. The only exceptions are: 1) when the subject is a responder both before and after the visit window, the subject will be categorized as a responder for the visit. 2) missing data due to COVID-19 infection or logistical restriction will be handled by Multiple Imputation. Of note, the intercurrent events of initiation of antibiotics for HS-related infections or discontinuation of study drug due to lack of efficacy will lead the subjects being counted as non-responders at later visits. Subjects whose change/percent change from Baseline cannot be calculated because of a missing Baseline will be considered as non-responders at all post-baseline visits. When determining the HiSCR response status, a subject with missing Baseline value will be counted as a non-responder at any post-baseline visit unless a subject's abscess, inflammatory nodule, and draining fistula counts are all zero at a specific visit, where the subject will be a HiSCR responder at that visit. More details are provided in [Appendix E](#).

- A sensitivity analysis for categorical endpoints will use **NRI** with **No** special data handling for missing due to **COVID-19 (NRI-NC)**.

NRI-NC will be performed in the same way as NRI-C without the exception #2 above. That is, missing due to COVID-19 infection or logistical restriction will also be counted as non-responders.

The NRI-C and NRI-NC will not be applicable to experience of flare in Period 1 since it is event-driven.

- Multiple Imputation (MI), a sensitivity analysis for the primary endpoint. Markov Chain Monte Carlo (MCMC) will be first applied to augment data into monotonic missing pattern and PROC MI will be used to generate 30 datasets using the regression method. Taking abscess count as an example, the variables to be included in the imputation model are: major stratum (prior exposure to anti-TNF [yes, no], Hurley Stage [< III, III]), Baseline, and measurements at each visit up to the end of the Period 1. The random seed for MCMC and the random seed for PROC MI are specified in [Appendix D](#). The imputed post-baseline measurements will be rounded to the same precision as the observed data. The same imputation strategy will be applied to the inflammatory nodule count and the draining fistula count. HiSCR status will be determined accordingly. Using the one sample Chi-square test, the imputed endpoint will be analyzed using each of the 30 datasets. A pooled test statistic from the chi-square distributed statistics after analyzing each of the 30 imputed datasets will be used to test the difference between upadacitinib group and historical placebo rate with Rubin's strategy. Note that measurements will be considered as missing after receiving antibiotics for HS-related infections or discontinued study drug due to lack of efficacy before MI. Regardless of MI imputed values, subjects receiving antibiotics for HS-related infections or discontinued study drug due to lack of efficacy will be counted as non-responders at later visits.

9.2.2 Continuous Endpoints in Period 1

For continuous endpoints except for DLQI, missing data will be handled using Mixed-Effect Model Repeat Measurement (MMRM).

- MMRM will be conducted using a mixed effect model including observed measurements at all visits. For the comparison with historical placebo change

from Baseline, the dependent variable is change from Baseline, and the mixed model for Period 1 includes visit, main stratification factors at randomization (prior exposure to anti-TNF [yes, no], Hurley Stage [<III, III]), and the corresponding Baseline as a continuous variable. For the comparison with in-trial placebo data, the dependent variable is change from Baseline, and the mixed effect model for Period 1 includes treatment, visit, treatment by visit interaction, main stratification factors at randomization, and the corresponding Baseline as a continuous variable. Subjects' observations after receiving antibiotics for HS-related infections or discontinued study drug due to lack of efficacy will be excluded from the analysis. An unstructured variance covariance matrix (UN) will be used. If the model cannot converge, an appropriate covariance structure matrix (e.g., autoregressive (1) or compound symmetry) will be used. The parameter estimations are based on the method of restrictive maximum likelihood (REML). The fixed effects will be used to report model-based means at corresponding visits.

No missing data handling will be used for DLQI in Period 1 since there is only one post-baseline assessment in Period 1. An ANCOVA model will be applied. For the comparison with historical placebo change from Baseline, the dependent variable is change from Baseline in DLQI, and the model includes main stratification factors and the corresponding Baseline as a continuous variable. For the comparison with in-trial placebo data, the dependent variable is change from Baseline in DLQI, and the model includes treatment, main stratification factors and the corresponding Baseline as a continuous variable.

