Comparison between the in-trial data of the upadacitinib group and the in-trial placebo subjects will also be performed. The analysis method will be the same as described above.

The NRI-C will be the primary approach for missing data handling in the analysis of the primary efficacy endpoint. NRI-NC and MI will be used as sensitivity analysis.

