2.3 Imputation Algorithm

It is reasonable to assume the missing values of the longitudinal data for an outcome variable (e.g., abscess count at each post-baseline visit) follows a monotone missing pattern. In practice, the missing data of the outcome variable might have an arbitrary (non-monotone) missing data pattern. An extra step may be added accordingly, to augment data into a monotone missing pattern.

For the outcome variable (e.g., abscess count at each visit), K 'complete' datasets can be generated in two steps: augmentation step and imputation step. K, the number of repetitions, is determined below.

Augmentation Step

For datasets with non-monotone missing data pattern, the augmentation step will first impute enough values to augment the data into a monotonic missing pattern:

Markov Chain Monte Carlo (MCMC) will be applied to augment the data using PROC MI with the MCMC IMPUTE=monotone statement, assuming a multivariate normal distribution. The augmented data will be used in the subsequent imputation step to generate 'complete' datasets. Covariates included in the model are treatment group, prior

exposure to anti-TNF category, Baseline Hurley Stage, Baseline abscess count, all post-baseline visits of abscess count up to the end of the Study Period. Of note, categorical variables are included using the form of dummy variables.

Repeat the imputation process $K=30$ times using the procedure described above to form $K=30$ monotone missing datasets, where K is determined as described in "Repetition of Imputations (K)."

Imputation Step

For missing data with monotone missing patterns, the choice of multiple imputation using a parametric regression model that assumes multivariate normality is appropriate.

The imputation step is described below:

- The imputation model for the missing data is a regression model, which controls for treatment group, prior exposure to anti-TNF category, Baseline Hurley Stage, Baseline abscess count, all post-baseline visits of abscess count up to the end of the Study Period. The covariates included in the model and the order of these variables are consistent with the augmentation step.
- For each monotone missing dataset, using SAS PROC MI with MONOTONE REG model statement, the outcome variable at each post-baseline visit with missing values will be imputed sequentially with covariates constructed from their corresponding sets of preceding variables.

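### The MI variable list in SAP 9.2.1 omits treatment group and conflicts with Appendix E; if followed literally with both arms pooled, the effect is small for the test against 25% and larger for the in-trial placebo comparison

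*SAP*

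**What the plan says.** SAP 9.2.1 describes MI as a sensitivity analysis for the primary endpoint. An MCMC step makes the missing pattern monotone, and then "PROC MI will be used to generate 30 datasets using the regression method". Taking abscess count as its example, it states that "the variables to be included in the imputation model are: major stratum (prior exposure to anti-TNF [yes, no], Hurley Stage [< III, III", followed by "Baseline, and measurements at each visit up to the end of the Period 1". The same strategy applies to inflammatory nodules and draining fistulas. Treatment group is not named, and the text does not say whether the arms are imputed together or separately. The only test it describes is one-sample: the pooled statistic "will be used to test the difference between upadacitinib group and historical placebo rate with Rubin's strategy".

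Appendix E, written for NRI-C, imputes the same counts with a regression model "which controls for treatment group, prior exposure to anti-TNF category, Baseline Hurley Stage, Baseline abscess count" and the post-baseline visits. Treatment group is also a covariate in its augmentation step. The sample code in Appendix E 3.0 carries the treatment variable in both PROC MI calls.

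SAP 9.3.3 sets out the comparisons of upadacitinib with in-trial placebo, with and without historical placebo subjects, and closes by saying that "NRI-NC and MI will be used as sensitivity analysis". Appendix D gives MI its own seeds (list B), separate from those for NRI-C (list A).

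**The concern.** If an imputation model leaves out the factor being compared and is fitted to both arms together, missing subjects in both arms are drawn from one shared distribution. Imputed upadacitinib values move toward placebo and imputed placebo values toward upadacitinib.

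This matters because of what MI is for. NRI-C and NRI-NC both set missing values not due to COVID-19 to non-response. MI is the one planned analysis of the primary endpoint that does not, so it is the check on whether that rule drives the result. In a two-arm comparison, an MI that shrinks the difference could appear to confirm the non-responder result simply by reproducing its attenuation.

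**Working it through.** **Inputs.** 57% on upadacitinib, 25% historical placebo, 40 upadacitinib subjects, one-sided alpha 0.05 (Protocol 7.7, SAP 2.4); 2:1 allocation, 40 and 20 (SAP 2.2). For the two-arm figures I assume a true in-trial placebo rate of 25%. Neither document plans a dropout rate. Appendix E 2.3 mentions only that less than 30% missing information is usual, so 10%, 20% and 30% missing are assumptions.

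**The plan's own figure.** One-sample power = Φ{[p1 − p0 − 1.645·√(p0(1−p0)/n)] / √(p1(1−p1)/n)}
= Φ{[0.32 − 1.645 × 0.0685] / 0.0783} = Φ(2.65) = 99.6%.
This agrees with the stated more than 95%.

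**Bound if treatment is omitted and the arms are pooled.** A missing subject with no post-baseline data is drawn at about the pooled rate, (40 × 0.57 + 20 × 0.25)/60 = 27.8/60 = 46.3%. With a fraction m missing in each arm:
- upadacitinib = (1 − m) × 57% + m × 46.3%
- placebo = (1 − m) × 25% + m × 46.3%
- difference between arms = (1 − m) × 32 points

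| Missing | Upadacitinib | Loss from 57% | One-sample power | Placebo | Two-arm difference |
|---|---|---|---|---|---|
| 10% | 55.9% | 1.1 | 99.4% | 27.1% | 28.8 |
| 20% | 54.9% | 2.1 | 99.1% | 29.3% | 25.6 |
| 30% | 53.8% | 3.2 | 98.7% | 31.4% | 22.4 |

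Approximate one-sided power for 40 versus 20, ignoring strata and treating imputed values as observed, is Φ{[d − 1.645·√(0.463 × 0.537 × (1/40 + 1/20))] / √(pU(1−pU)/40 + pP(1−pP)/20)}. With complete data it is Φ{(0.320 − 0.225)/0.125} = 78%. At the 20% bound it is Φ{(0.256 − 0.225)/0.129} = 60%.

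**Effect of earlier visits.** I simulated latent normal scores at Weeks 2, 4, 8 and 12 (correlation 0.6 between adjacent visits, treatment effect growing over time), with sequential regression imputation and 400 trials of 40 and 20. Monte Carlo error is about 0.4 point for upadacitinib and more for placebo. Results at 20% missing, upadacitinib / placebo:

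| Last visit observed | Without treatment | Difference | With treatment | Difference |
|---|---|---|---|---|
| None after Baseline | 55.2 / 29.0 | 26.2 | 57.0 / 26.8 | 30.2 |
| Week 2 | 54.8 / 29.2 | 25.6 | 56.6 / 25.6 | 31.0 |
| Week 8 | 56.5 / 26.7 | 29.8 | 57.6 / 25.6 | 32.0 |

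Without treatment the difference is about 26 to 30 points, and nearer the true 32 when later visits are observed. When only the upadacitinib arm was imputed, without a treatment term, its rate was 56.5 to 56.9%, essentially unbiased.

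**MI beside non-responder imputation at 20% missing.** Suppose no missingness is due to COVID-19. Non-responder imputation gives 0.8 × 57 = 45.6% and 0.8 × 25 = 20.0%, a difference of 25.6 points. Pooled MI at the bound also gives 25.6, whereas correct MI gives 32. Against the fixed 25% the margins are 20.6 points for non-responder imputation, 29.9 for pooled MI and 32 for correct MI, so there MI still works as a check.

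**The case against.** A reader might infer that the MI analysis does omit treatment and is therefore biased toward no difference. The documents do not support that as fact. Both PROC MI steps in the sample code include treatment, and the comment placed after the imputation tells the MI analysis to skip the non-responder override that follows. MI thus appears to share the imputation code and drop only the override. Separate seeds make MI a separate run, not necessarily a separate model. This stands.

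A reader might also apply the shrinkage of the two-arm difference to the test in 9.2.1. That test compares upadacitinib with a constant, so imputed placebo values do not enter it. If only the upadacitinib arm were imputed, leaving treatment out would be harmless. The mixed models in 9.2.2 follow that pattern: no treatment term against the historical value, and one against in-trial placebo. This stands too, but 9.2.1 does not restrict imputation to one arm, and a comment in the sample code calls for all data in the imputation model.

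That MI covers the in-trial comparison is an inference from the position of its mention in 9.3.3. Two-sample pooling appears only in Appendix E, beside a model that includes treatment.

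Finally, the size is overstated to the extent that the override applies. It reads "Regardless of MI imputed values, subjects receiving antibiotics for HS-related infections or discontinued study drug due to lack of efficacy" and counts these subjects as non-responders at later visits. Neither the bound nor the simulation includes it.

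What remains is the conflict in the text. Appendix E is titled for NRI-C, the MI paragraph refers only to Appendix D for its seeds, and the sample code shows NRI-C seeds. A code comment does not clearly override an explicit variable list.

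**Conclusion.** The inconsistency is real and minor. SAP 9.2.1 lists an imputation model without treatment group, and Appendix E gives one with it for the same counts.

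The numerical consequence is conditional on the 9.2.1 list being run literally on both arms together. The test against 25% then loses at most about 1 to 2 points at an assumed 10 to 20% missing, with power about 99%. The in-trial difference falls from 32 to about 26 to 30 points at an assumed 20% missing, and there MI would lose much of its value as a check on non-responder imputation. These figures rest on assumed missing fractions, equal missingness in the two arms, and a latent normal model.

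The primary NRI-C analysis explicitly includes treatment and is unaffected. Any bias in MI would be toward no difference.

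**What to change.** In SAP 9.2.1, add treatment group to the MCMC and regression steps for abscess, inflammatory nodule and draining fistula counts. Alternatively, state that MI uses the Appendix E 2.3 imputation model with the Appendix D (B) seeds. Either costs one phrase and needs no new data. It should be settled before the Week 12 database lock.

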9.2.3 Summary of Long-Term Efficacy

Long-term efficacy in the Period 2 will be summarized using the observed case approach.

- Observed Case (OC) while on study drug: The OC analysis will be used for the summaries of long-term efficacy, which will not impute values for missing evaluations, and thus a subject who does not have an evaluation on a scheduled visit will not be included in the OC analysis for that visit. The OC analysis will be performed for all variables and will not include values after subjects

receiving antibiotics for HS-related infections or discontinued study drug due to lack of efficacy.

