5.4 Prior and Concomitant Therapy

Any medication or vaccine (including over-the-counter or prescription medicines, vitamins and/or herbal supplements) that the subject is receiving at the time of screening, and/or receives during the study, must be recorded along with the reason for use, date(s) of administration including start and end dates, and dosage information including dose, route and frequency on the appropriate electronic case report form (eCRF). Also, medications taken for HS since date of diagnosis (based on subject recollection and available medical records) should be entered into the appropriate eCRF inclusive of the dates of first and last dose, maximum dosage taken, route of administration.

Any questions regarding concomitant or prior therapy should be raised to the AbbVie Therapeutic Area Medical Director (TA MD)/AbbVie emergency contact. Information regarding potential drug interactions with upadacitinib can be located in the upadacitinib Investigator's Brochure.

Allowed Therapies

Antibiotics

Concomitant use of antibiotics is allowed for the treatment of acute infections during the study. Use of topical or systemic antibiotics to treat HS or other chronic inflammatory disorders is prohibited up to Week 16. After Week 16, concomitant use of any antibiotics for any indication, including HS, is permitted.

Dosing and/or frequency need to be reported in the eCRF documentation; "as needed" (PRN) use is not permitted.

Antiseptic Wash

Subjects are required to use a daily antiseptic wash on their HS lesions for the duration of the study.

Allowable antiseptic washes are limited to: chlorhexidine gluconate, benzoyl peroxide, benzalkonium chloride, or dilute bleach in bathwater.

Wound Care

Use of wound care dressings on HS wounds is allowed. Recommended options include alginates, hydrocolloids, and hydrogels.

Lesion Intervention

Deroofing or STEEP, laser therapy, intense pulse light, local/wide/radical excision, incision and/or draining of lesions, and intralesional injections are allowed after Week 16 assessments. Refer to Section 6.2 for study drug interruption guidelines for elective and emergency surgeries.

Analgesic therapy

If a subject experiences pain (HS- related or non-HS-related) after Baseline, they may initiate analgesic treatment. For HS-related pain, analgesic therapy is limited to the following until after the Week 16 assessments:

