5.6 Follow-Up After Subject Discontinuation of Study Drug or from Study

Discontinuation of Study Drug and Continuation of Study Participation

To minimize missing data for efficacy and safety assessments, subjects who prematurely discontinue study drug treatment should continue to be followed for all regularly scheduled visits as outlined in the Activity Schedule (Appendix D), unless subjects have decided to discontinue study participation entirely (withdrawal of informed consent). Subjects should be advised on the continued scientific importance of their data even if they discontinue treatment with study drug early. Following discontinuation of study drug, the subject should be treated in accordance with the investigator's best clinical judgment irrespective of whether the subject decides to continue participation in the study.

Premature Discontinuation of Study (Withdrawal of Informed Consent)

If a subject prematurely discontinues study participation (withdrawal of informed consent), the procedures outlined for the Premature Discontinuation visit should be completed as soon as possible, preferably within 2 weeks. In addition, if subject is willing, a 30-day follow-up visit (or phone call if a visit is not possible) after the last dose of study drug may be completed to determine the status of any ongoing AEs/serious adverse events (SAEs) or the occurrence of any new AEs/SAEs.

For subjects to be considered lost to follow-up, reasonable attempts must be made to obtain information on the subject's final status. At a minimum, 2 telephone calls must be made and 1 certified letter must be sent and documented in the subject's source documentation.

In the event a subject withdraws consent from the clinical study, biomarker research will continue unless the subject explicitly requests analysis to be stopped. When AbbVie is informed that samples are withdrawn from research, samples will not be analyzed, no new biomarker analysis data will be collected, and the samples will be destroyed. A subject may withdraw consent for optional biomarker research at any time and remain in the clinical study. Data generated from clinical study and/or optional biomarker research, before subject withdrawal of consent, will remain part of the study results.

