8.0 Handling of Potential Intercurrent Events for the Primary Endpoint

The primary efficacy endpoint, achievement of HiCSR at Week 12 (defined in Section 3.1) will be analyzed in the ITT Population and the following method will be used to address potential intercurrent events:

- Intercurrent events of initiation of antibiotics for HS-related infections and discontinuation of study drug due to lack of efficacy before Week 12 are included in the definition of primary endpoint; subjects who have either intercurrents above will be considered not achieving the response. No other intercurrent events are considered.

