9.5.3 Summary of Long-Term Efficacy

Long-term efficacy in Period 2 will be summarized by visit for ITT Population using the observed case approach, as described in Section [9.2.3](#).

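### Period 2 efficacy is summarised only by observed case, which drops subjects after two events that Period 1 counts as non-response, so the by-visit response series changes definition after Week 12

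*SAP*

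**What the plan says.** SAP 9.5.3 sets the method: "Long-term efficacy in Period 2 will be summarized by visit for ITT Population using the observed case approach". SAP 9.1 names the same approach, and neither section adds another.

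SAP 9.2.3 defines it. Nothing is imputed, and "a subject who does not have an evaluation on a scheduled visit will not be included in the OC analysis for that visit". The next sentence goes further than ordinary observed case. It applies to every variable and drops whatever was recorded later than either of two events, which it gives as "receiving antibiotics for HS-related infections or discontinued study drug due to lack of efficacy".

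In Period 1 these two events are handled differently. SAP 9.2.1 says that they "will lead the subjects being counted as non-responders at later visits", and SAP 8.0 says of the primary endpoint that "subjects who have either intercurrents above will be considered not achieving the response". NRI-C, NRI-NC and multiple imputation are specified for Period 1 only.

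Two protocol rules bear on this. Section 5.4 says: "After Week 16, concomitant use of any antibiotics for any indication, including HS, is permitted". Section 5.6 says that subjects who stop study drug early "should continue to be followed for all regularly scheduled visits as outlined in the Activity Schedule", so values after a lack-of-efficacy stop may well have been collected.

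**The concern.** HiSCR and NRS30 are to be analysed at every visit where they are measured (Protocol 3.3, SAP 3.3), so a reader will naturally follow the rate from Week 12 into Period 2. Up to Week 12 a subject with either event stays in the denominator as a failure. From Week 16 that subject is in neither numerator nor denominator. A subject whose event fell in Period 1 is a non-responder at Week 12 and is then absent at Week 16, because all of that subject's Period 2 values come after the event.

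At stake is how statements about maintenance of response are read. A flat or rising curve could reflect lasting benefit, or the removal of subjects in whom treatment had failed, and the planned table would not let the reader tell which.

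**Working it through.** **Plan's own figures.** The documents state no figure for Period 2. The nearest planning figure is the 57% HiSCR rate assumed for 30 mg in SAP 2.4, where 40 subjects are said to give more than 95% power against 25% (one-sided 0.05). That reproduces: (0.32 × √40 − 1.645 × √(0.25 × 0.75)) / √(0.57 × 0.43) = (2.024 − 0.712) / 0.495 = 2.65, a power of 99.6%. It concerns Week 12 only and is not in question. The 57% serves below as a starting point.

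**Inputs.**
- N = 40 on 30 mg (SAP 2.2). Assumed: all enter Period 2 and nothing else is missing.
- r = responders still counted. Assumed 23, since 23/40 = 57.5%, close to 57%.
- f = subjects removed after either event. Not in the documents. Assumed 4, 8 or 12 (10%, 20%, 30%).

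**Formulas.** Observed case = r/(N − f). Composite = r/N. Their ratio is N/(N − f), which exceeds 1 whenever f > 0. With r > 0, observed case is therefore always the higher of the two.

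**Case 1: every removed subject is a non-responder.**

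| Removed | Observed case | Composite | Difference (points) |
|---|---|---|---|
| 4 | 23/36 = 63.9% | 57.5% | 6.4 |
| 8 | 23/32 = 71.9% | 57.5% | 14.4 |
| 12 | 23/28 = 82.1% | 57.5% | 24.6 |

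No subject improves in any row. If the 4 subjects in the first row had their events before Week 12, the rate would step from 57.5% at Week 12 to 63.9% at Week 16 with no clinical change.

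For the placebo-to-15 mg arm (N = 20, 11 responders assumed, composite 55.0%), removing 2, 4 or 6 gives 11/18 = 61.1%, 11/16 = 68.8% and 11/14 = 78.6%.

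**Case 2: some removed subjects are responders by lesion count.** Take 23 responders by count among 40, with 8 removed, m of them responders. The rate using all observed values is 23/40 = 57.5%.
- m = 4: observed case 19/32 = 59.4%, composite 19/40 = 47.5%.
- m = 5: observed case 18/32 = 56.2%, composite 18/40 = 45.0%.

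Observed case stays above the composite in both. Against all observed values it is higher at m = 4 and lower at m = 5. That second comparison depends on who is removed.

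**Visits affected.** Protocol Appendix D and the Week 48 list in Operations Manual 2.1 include no lesion count at Week 48, so HiSCR ends at Week 40. Skin pain is collected to Week 48.

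**The case against.** The best defence has four parts.

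- **Period 2 is descriptive.** The hypothesis, estimand, power and primary test concern Week 12, and there is no placebo arm afterwards. This stands, and it limits the weight of the point.
- **An on-treatment summary may leave out subjects who stopped.** SAP 9.2.3 labels the method as covering time on study drug, and response among those still treated is a fair question. This stands for subjects who stopped for lack of efficacy. It does not cover subjects who take antibiotics and stay on drug, whose observed values are also removed. Nor does the text match the label, since stops for other reasons trigger no stated exclusion.
- **The Period 1 rule does not carry over automatically.** Antibiotics for HS are prohibited up to Week 16 and permitted afterwards, so counting a permitted course as failure at every later visit may understate response. The SAP trigger, HS-related infections, is also narrower than the protocol's permission, and its frequency is unknown. This stands, and it is why the added table should be supplementary.
- **Attrition is reported elsewhere.** SAP 5.0 gives Period 2 discontinuations by reason, and SAP 7.3 summarises concomitant medication. Neither shows how many subjects left a given visit's rate, or why.

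A reader might infer that the Period 2 curve must rise as treatment fails. The documents do not support that: case 2 shows that the rate can fall below the all-observed rate if enough removed subjects were responders.

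**Conclusion.** The point holds as an inconsistency of definition within one by-visit series. The observed-case rate exceeds the composite rate whenever anyone is removed and a responder remains, which follows from the formulas alone. The size does not: the gaps of 6.4, 14.4 and 24.6 points rest on assumed event shares of 10% to 30%, on every removed subject being a non-responder, and on no other missing data. They are illustrations, not estimates.

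Three further readings are tempting and not supported. The Week 12 primary result is not affected, because its composite rule is explicit. This is not a 48-week HiSCR result, because lesion counts stop at Week 40. And the trial is not unable to describe durability: visits are meant to continue after drug is stopped, so the limitation lies in the planned summary. The point merits a modest SAP change.

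**What to change.** Keep the observed-case table, and print beside each rate the n and the number excluded by reason: antibiotics for an HS-related infection, lack-of-efficacy stop, or no evaluation. State in SAP 9.2.3 whether values after stops for other reasons are included.

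Add a supplementary by-visit table for HiSCR (Weeks 16 to 40) and NRS30 (to Week 48):
- The denominator is all subjects who entered Period 2; for NRS30, those among them with baseline NRS of at least 3, as the endpoint requires.
- Either event counts as non-response at later visits.
- The rule for other missing data is stated, for example non-response, with COVID-19 missingness shown separately.
- For NRS30, the day-level analgesic rule of SAP 9.4.1 is not applied after Week 16, when the daily diary ends.

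Any statement about maintenance of response should be read alongside this table.

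The cost is SAP wording and one table, with no new data, visits or subjects. The downside is a lower long-term rate, which may be conservative because antibiotics for HS are permitted after Week 16. A footnote should say so.
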